1.2 SAMPLE SIZE DETERMINATION AND POWER CALCULATIONS

Aim 1

We calculate that the study will have an 80% or greater power to detect a significant difference in the proportion of HIV testing associated with the intervention arm, assuming a proportion self-testing in the control arm of 38% (observed data from SEARCH in fishermen) if the proportion testing in the intervention arm is 52% or greater (odds ratio of 1.8), calculated using an Intraclass Correlation Coefficient (ICC) of 0.15 (conservative based on SEARCH data), 70 clusters each in the intervention and control arms, average cluster size of 7 in both arms, and a type-1 error rate of 5%.^{125,126} Figure 2 shows statistical power and the range of detectable odds ratios over extremes of clustering effects.

Aim 2

For the Aim 2 combined primary outcome of successful linkage to ART or PrEP within 3 months of intervention start (+about 1 month), this study will have a 80% or greater power to detect a significant increase in successful linkage, assuming a proportion successfully linked at 3 months in the control arm of 24% (based on observed SEARCH trial linkage rates weighted for the number of eligible PrEP HIV-negative men and HIV-positive men not currently in HIV care) if the observed proportion in the intervention arm is 39% or greater (odds ratio of 2.0), using an ICC of 0.15, 70 clusters each in intervention and control arms, a cluster size of 7 in both arms, and a type-1 error rate of 5%. Statistical power for combined ART or PrEP

start is similar, with a reduction in anticipated eligible numbers per cluster reduced to 6 resulting in a small increase in the detectable odds ratio to 2.2 or greater. Power for a separate analysis of ART initiation alone is likely to be low given the small numbers of new HIV infections in the study sample with odds ratios in excess of three or four required.

Aim 3

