For the primary outcome, we will have \geq 80% power to detect a significant increase in viral suppression and adherence in those on ART and PrEP, respectively, assuming a proportion of successes in the control arm of 70% or greater power (*based on SEARCH trial data on viral suppression rates among fishermen and projected urine TFV detection rates of 70%, weighted for the likely number of men on PrEP (n=168) and men on ART (n=72)*). We assume the observed proportion of successes in the intervention arm will be 89% or greater using an ICC of 0.10, a design effect from clustering of 1.7, and a type-1 error rate of 5%. For the combined primary outcome of retention on ART or PrEP at 6 months (+ about 1 month), this study will have 81% or greater power to detect a significant increase in linkage assuming a proportion retained in care in control arm of 81% (*based on SEARCH data on retention rates weighted for the likely number of men on PrEP (n=168) and ART (n=72)*) if the observed proportion in intervention arm is 96% or greater using the above assumptions.

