1.3.3 ANALYSIS OF ADDITIONAL ENDPOINT(S)

Primary Outcome: the primary outcome measure will be linkage to care or prevention within 3 months of the Aim 1 intervention start. Linkage will be defined for HIV-positive participants as a documented confirmatory HIV test result, and a documented HIV clinic visit following referral. Linkage will be defined for HIV-negative participants as documented evidence of evaluation for PrEP (following standard of care procedures) extracted from medical records.

Secondary outcome: The secondary outcomes will be confirmatory HIV testing uptake 3 – 6 months after intervention start and the initiation of ART, or PrEP (among those screened as eligible), within 3 months of the confirmatory test or eligibility screening. HIV testing uptake will be measured via documented testing records in clinic records and ART start will be measured via documented prescription for ARV medications, and for PrEP start, via oral PrEP prescription.

Third outcome: The third primary outcome is a composite measure meant to capture "success" in HIV prevention and/or treatment behaviors. The measure will be defined as either adequate levels of tenofovir, indicating PrEP adherence (defined as TFV levels of >= 1500 ng/mL in urine indicating adequate adherence vs. < 1500 ng/ml) among HIV seronegative individuals who screened eligible for PrEP or the proportion of HIV-positive participants with viral suppression (defined as HIV RNA <400 c/mL using the Abbott realTime HIV-1 platform and assay, with a detectable threshold of 40 cells per microliter at 6 months. PrEP adherence will be measured at 6 months after initiation using our novel technology of point-of-care rapid testing to assess TFV adherence in urine (developed by Co-I [name] in collaboration with Alere Rapid Diagnostics[™]). For both components of the measure, we will define missing values as failure (i.e. inadequate adherence or unsuppressed).

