Analytic Plan: For the test of the *social network-central promoters and small incentive* intervention effect on the primary outcome of linkage to care or prevention within 3 months of intervention start we will utilize a cluster adjusted Pearson's Chi-square test comparing the proportion of subjects with documented linkage to care or prevention in the intervention versus the control arm. In secondary analysis, we will utilize multilevel mixed-effects logistic regression as described in Aim 1 to investigate factors that influence the probability of success of linkage to care and prevention. We will also evaluate the secondary outcomes of ART initiation among HIV-positive persons not currently on treatment, and initiation of PrEP among HIV-negative persons who screen as eligible. We will compare the initiation proportions between study arms using cluster adjusted Chi-square tests and additional multilevel mixed-effects logistic regression to identify influencing factors.

We will measure the combined outcome of 1) Proportion of HIV-positive participants with viral suppression (HIV RNA <400 c/mL) at 6 months missing=failure (unsuppressed) and 2) Proportion of participants adherent to PrEP (TFV levels of >=1500 ng/mL in urine indicating adequate adherence) at 6

months missing=failure (nonadherent). PrEP adherence will be measured at 6 and 12 months after initiation using our novel technology of *point-of-care rapid testing to assess TFV adherence in urine*). (+ about 1 month for all measures)

Secondary Outcomes: HIV testing uptake 3 to 6 months after intervention start and retention on ART at 6 months or PrEP at 6 months. Using clinic records, we will assess whether men had confirmatory HIV testing and those who initiated PrEP and ART attended scheduled appointments and record VL results. (+ about 1 month for all measures)

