Analytic approach: We will utilize a cluster adjusted Pearson's Chi-square test comparing the proportion of successes (HIV viral suppression and adequate TFV levels) among men (on ART and PrEP, respectively) in the intervention and control networks. For the outcome of retention on ART or PrEP at 6 months. We will utilize a cluster adjusted Pearson's Chi-square test comparing the proportion of subjects on ART or PrEP at 3 months post trial start who are retained in care at 6 months in intervention versus control group. In secondary analysis, we will utilize Cox proportional hazards regression to investigate factors that influence time to discontinuation of ART or PrEP We will also use multilevel mixed-effects logistic regression to investigate factors that influence the probability of viral suppression and TFV detection in urine. (+ about 1 month for all measures)

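### The Aim 3 primary test pools viral suppression on ART with tenofovir adherence on PrEP without stratifying, so a difference between arms in the ART/PrEP mix can shift the result by itself

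*Protocol*

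**What the plan says.** In protocol 1.3.3, "The third primary outcome is a composite measure". For HIV-negative men, success is a urine tenofovir (TFV) level of at least 1500 ng/mL. For HIV-positive men, it is HIV RNA below 400 c/mL. The analytic plan in the same section repeats the combination: "We will measure the combined outcome of 1) Proportion of HIV-positive participants with viral suppression" is listed with PrEP adherence as the second part, and missing values count as failures in both. The test is a cluster-adjusted Pearson chi-square "comparing the proportion of successes (HIV viral suppression and adequate TFV levels) among men (on ART and PrEP, respectively"). SAP item 27(c) uses the same test.

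Neither document attaches a stratum, a fixed weighting or a separate primary test per component to this comparison. SAP item 27 lists sensitivity analyses as not applicable and subgroup analyses as NA.

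The sample size section (protocol 1.2, Aim 3) does use a mix. The control rate is "weighted for the likely number of men on PrEP (n=168) and men on ART (n=72"), stated as "assuming a proportion of successes in the control arm of 70% or greater power", and is "based on SEARCH trial data on viral suppression rates among fishermen and projected urine TFV detection rates of 70"%. For the other arm: "We assume the observed proportion of successes in the intervention arm will be 89% or greater using an ICC of 0.10", with a design effect of 1.7. No suppression rate is given separately.

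**The concern.** Networks are randomised, but membership of the Aim 3 comparison is not. A man enters it by starting ART or PrEP, and protocol 1.1 hypothesises that the intervention raises uptake of both. The share of ART men in each arm is therefore itself affected by the intervention. If that share differs between arms, and suppression on ART is not as frequent as adherence on PrEP, the pooled proportions differ even when neither component has changed. A real benefit could be diluted, or a small difference could appear with no effect behind it. The planning calculation fixes the mix at 72 to 168; the test does not carry that weighting forward. This is distinct from selection into treatment, because it operates even when the men within each component are comparable across arms.

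**Working it through.** **1. The plan's own power figure.** Inputs from protocol 1.2: 168 + 72 = 240 men, 70% v 89%, design effect 1.7. SAP item 16 gives two-sided 5%. Assume 120 men per arm, so 120 / 1.7 = 70.6 effective per arm.

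Power = Φ[(0.19 − 1.96 × √(2 × 0.795 × 0.205 / 70.6)) / √((0.70 × 0.30 + 0.89 × 0.11) / 70.6)] = Φ[(0.190 − 0.133) / 0.066] = 80.5%.

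The stated 80% or more reproduces and is not in dispute.

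**2. Formula for the shift.** With ART share w, suppression rate pV and adherence rate pT, an arm's pooled rate is w·pV + (1 − w)·pT. If pV and pT are the same in both arms, the pooled difference is (w_int − w_con) × (pV − pT). It vanishes if either factor is zero.

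**3. Component rates.** Taken literally, a pooled 70% with TFV at 70% and weights 30:70 gives 0.3·pV + 0.7 × 0.70 = 0.70, so pV = 70% and there is no shift. TFV 70% is only a projection, however, and suppression is not stated. Holding just the 70% average, pT = (0.70 − 0.3·pV) / 0.7. That gives 65.7%, 63.6% and 61.4% for assumed pV of 80%, 85% and 90%.

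**4. Mix by arm (assumed).** The Aim 2 linkage rates of 24% and 39% split 240 men as 240 × 24/63 ≈ 91 and 149. Two allocations fit the totals of 72 and 168:
- *Proportional uptake:* ART 27 v 45, PrEP 64 v 104. ART share is 29.7% v 30.2%. For the rates above the shift is at most 0.005 × 28.6 ≈ 0.15 points, so effectively none.
- *All extra uptake on PrEP:* ART 36 v 36, PrEP 55 v 113. ART share is 39.6% v 24.2%, a gap of −15.4 points.

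**5. Results when all extra uptake is PrEP.** Type I error and power come from simulation (200,000 runs, counts divided by 1.7). The planned effect is applied as a common odds ratio of (0.89/0.11) / (0.70/0.30) = 3.47 in both components.

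| Suppression / TFV | Pooled, control v intervention, no effect | Shift (points) | Type I error, pooled test | Power, pooled | Power, stratified |
|---|---|---|---|---|---|
| 70% / 70% | 70.0% v 70.0% | 0 | about 5% | 81% | 79% |
| 80% / 65.7% | 71.4% v 69.2% | −2.2 | about 6% | 73% | 78% |
| 85% / 63.6% | 72.1% v 68.8% | −3.3 | about 7% | 67% | 78% |
| 90% / 61.4% | 72.7% v 68.3% | −4.4 | about 8% | 62% | 77% |

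Nearly all the excess type I error is in the direction of apparent harm. A Mantel-Haenszel test stratified by component stays at about 5% throughout.

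**6. Scale.** With 91 v 149 men the standard error of the pooled difference is √(0.70 × 0.30 × 1.7 × (1/91 + 1/149)) ≈ 7.9 points. The shift is therefore roughly 0.3 to 0.6 of a standard error.

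**7. Sign.** If suppression were below adherence (say 60% and 74.3%, again averaging 70%), the same mix would give −0.154 × −0.143 = +2.2 points.

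**The case against.** The strongest reply is that the shift needs two conditions, and the documents establish neither. The planning text can be read as 70% for both components, in which case nothing moves. Uptake rising in proportion in both groups fits the same totals, and again almost nothing moves. Both points stand, and the range must start at zero.

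A reader might infer that the extra uptake must be PrEP, because protocol 1.2 expects low power for ART initiation alone "given the small numbers of new HIV infections in the study sample". That remark concerns the power of a separate analysis. It does not say that ART uptake is the same in both arms, and protocol 1.1 hypothesises an increase in each. The 24:39 ratio is likewise a linkage ratio, not a ratio of men on treatment. The allocation used in the table is one possibility, chosen to show an unfavourable case.

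It can also be said that the components are partly covered. The synopsis lists suppression and PrEP adherence separately, SAP item 9 states a hypothesis for each, and secondary mixed-effects models look for factors that influence suppression and TFV detection. This helps, but none of it is a primary comparison by arm. SAP item 27(d) allows covariate adjustment, but for baseline non-equivalence or differential attrition, and within a model. The primary test is a chi-square, and this imbalance arises after baseline.

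Finally, stratifying by HIV status needs that status. It should be known for men on ART or PrEP, but not necessarily for every randomised man in the SAP's intention-to-treat population.

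**Conclusion.** The point holds as a weakness in the specification of the primary Aim 3 test. The test is unstratified, the mix is formed after randomisation, and nothing in either document fixes or adjusts it. The size is conditional. It is zero on the literal 70%/70% reading and negligible under proportional uptake. It is about −2 to −4 points, with type I error of about 6–8%, when rates average 70% but differ (suppression 80–90%) and all extra uptake is PrEP. The more practical loss is power: about 73% falling to 62% for the planned effect, where a stratified test keeps about 78% to 77%.

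A reader might infer that composition could account for a large part of the 19-point target, or that the pooled result is bound to be biased. The documents do not support that. A larger shift requires adherence well below the projected 70%, or a more extreme mix, and the direction is not fixed. The stated power figure is not in error.

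**What to change.** In protocol 1.3.3 and SAP item 27(c), make the Aim 3 primary test a cluster-adjusted comparison stratified by component (ART/HIV-positive v PrEP/HIV-negative). A Mantel-Haenszel risk difference would do, as would a regression with an HIV-status term and standard errors clustered by network. Report suppression and adherence by arm beside the composite.

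State that the comparison is among men on ART or PrEP, as the analytic approach has it. The outcome definition in the same section uses a different denominator (HIV-negative men who screened eligible for PrEP, and HIV-positive participants), and that choice also changes the mix, so the two must be reconciled first.

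The cost is wording, one extra term in the analysis and no new data for men on treatment. When the component rates are equal, stratifying loses at most about 2 points of power (81% to 79% in the table). With equal rates and a 30% ART share in both arms, the loss is under 1 point (82.4% to 81.8%, simulated with 71 effective men per arm). Stratifying does not deal with selection: the comparison is still between men who chose to start treatment in each arm, and the report should say so.

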1.3.4 ANALYSIS OF QUALITATIVE DATA

For the qualitative study aims throughout aims 1-3, we will conduct semi-structured in-depth interviews and FGDs in the local languages spoken in the region, by gender and language-matched trained qualitative researchers. Interviews will be conducted at a venues agreed upon by the participant while maintaining privacy and confidentiality. FGDs and Interviews will be audio recorded; recordings marked with study IDs will be transferred to secure servers and encrypted laptops for transcription, translation, and analysis. After FGDs and IDIs are conducted, the interviewers will transcribe and translate the audio recorded interviews into English and import into a qualitative software for analysis by the full team. The team will collaboratively develop an inductive coding framework on the basis of the interview/FGD guides and previous research. The inductive code list will be applied to the first set of transcripts; the team will meet periodically to review the coding framework and iteratively refine the coding framework, adding new codes through a deductive approach. Overlapping (blind coding) to achieve inter-rater reliability. All the qualitative interpretation activities will be guided by constructivist grounded theoretical approaches. Coding and analysis will take team-based approach to ensure rigor. We will use a two-phased analysis approach, beginning with: 1) qualitative analysis of in-depth and key informant interview and FGD data, using a grounded theoretical approach that involves iterative inductive coding of empirical data (transcripts); followed by a 2) mixed-methods analysis of qualitative data grouped by categories defined using social network survey data, process and fidelity measures, and trial outcome data. This will involve analyzing qualitative data collected within categorized groups of participants including (but not limited to) testers vs. non-testers, linkers vs. non-linkers to ART and PrEP, virally suppressed vs. detectable VL, and PrEP adherent vs. non-adherent. This approach will allow us to identify emergent themes within groupings and to rigorously assess conceptual alignment or differences across groupings, with attention to evidence of contradictory findings and deviant cases in the data.

2 STUDY INTERVENTION/EXPERIMENTAL MANIPULATION DISCONTINUATION AND PARTICIPANT DISCONTINUATION/WITHDRAWAL

2.1 DISCONTINUATION OF STUDY INTERVENTION/EXPERIMENTAL MANIPULATION

Participants who discontinue from the intervention will also be discontinued from the overall study; however they may continue to receive care at clinics according to country standard of care guidelines.

2.2 PARTICIPANT DISCONTINUATION/WITHDRAWAL FROM THE STUDY

Participants are free to withdraw from participation in the study at any time upon request. An investigator may discontinue a participant from the study for the following reasons:

- The participant meets a previously unrecognized exclusion criterion
- Significant non-compliance with the study
- Any event or situation that occurs such that continued participation would not be in the best interest of the participant

The reason for discontinuation and date of discontinuation will be documented in the study participant withdrawal/move case report forms (CRFs).

3 ETHICAL CONSIDERTATIONS

3.1 KNOWN POTENTIAL RISKS

HIV self-testing. Based on our own studies conducted in the past two years and several other studies, we believe there are relatively few risks to study participants. We have conducted research in the Nyanza region among female sex workers (FSW) as well as pregnant and postpartum women. Women in these studies were given multiple self-tests and encouraged to offer them to their male partners at their own discretion. One of our key objectives was to assess intimate partner violence (IPV) and other adverse events experienced by women. Our findings indicate that IPV and other adverse events were extremely rare – both for the women themselves and for their male partners who accepted and used the self-tests. These findings are consistent with other studies highlighted in WHO guidelines showing that self-tests are easy to use safely. The proposed study includes men only, who are rarely victims of IPV in this setting. The primary risk involved in study participation include emotional discomfort related to decision-making surrounding the decision to test for HIV and the receipt of test results in the absence of a counselor. HIV self-testing is designed reduce anxiety about testing for HIV because it enables self-test users to conduct the tests privately at a time and location of their choosing, and it does not require observation or help from others. However, as with any HIV testing research, if a study participant uses an HIV self-test or seeks clinic-based testing and obtains an HIV-positive test result, there is a risk of adverse reactions including psychological distress due to testing. There is also a risk that study participants may feel pressured by their peers to test and if they test, may be distressed by the results, especially if they obtain an HIV-positive result.

Our pilot study data indicate that women and their male partners reacted well to receiving their test results, even when a reactive result was obtained. These data are consistent with studies from sub-Saharan Africa showing that risks of adverse reactions following HIVST are very low. Proper information and subsequent counseling is nonetheless necessary to minimize the possibility of distress. We will put in place study procedures (described below) that are intended to minimize risks and address any adverse events that do occur. In our pilot study that implemented the intervention, we developed and used these procedures, and we also obtaining IRB approval for the procedures. Below we outline potential risks to study participants and the steps we are taking to minimize these risks.

In the close social network clusters assigned to the intervention, men will likely receive oral fluid-based HIV tests from the network central promoters who will receive multiple tests and be encouraged to offer them to other men in their networks. Each test will include instructions on how to use the oral fluid-based tests. Promoters will also be trained on test use so they can offer guidance to their male peers. We will provide detailed, easy-to-use instruction sheets on how to use self-tests as well as a demonstration to men at the time of enrollment on how to use self-tests, and a 'train the trainer' component to help them learn to instruct other men in the self-test usage.

Men in comparison networks will be asked to distribute (or attempt to distribute) referral vouchers that can be used to exchange for a free HIV self-test kit at the local study clinic, to the men in their close social networks. We will also provide detailed information to men in both groups on the need to seek clinicbased confirmatory testing after receiving an HIV-positive self-test result, as well as information on where individuals can receive care and treatment. Moreover, the study includes additional information about the benefits of screening for enrollment in HIV pre-exposure prophylaxis, for those who receiving an HIVnegative self-test result.

For the Aim 2 study, linkage to a local health facility for HIV care and treatment following confirmatory testing, and to PrEP eligibility screening, as well as uptake of either ART or PrEP, is measured for individuals in the Aim 1 study who report having used a self-test. In the intervention group only, incentives (vouchers to be exchanged for a small remuneration of the cost of transport to the local health facility), will be offered by network-central promoters to the men in their close social networks.

Network-central promoters in intervention clusters may be asked for HIV self-tests by individuals who are not part of their defined cluster (i.e. close social network) but are members of their community. Promoters may feel stress arising from not being able to comply with these requests. In our training of promoters and community sensitization and preparation, we will explain the purpose of the study carefully to ensure that promoters and members of communities understand that not all people in the community will receive HIV self-tests through the promoters. We will instruct the promoters to refer anyone interested in HIV testing to the nearest testing venue (the standard of care), and will ensure they have lists of appropriate nearby venues, including those where HIV self-tests are freely available. We will coach promoters in how to explain that they were given a limited number of self-tests for specific BMU members in their close social networks. In our experience with secondary distribution of HIV self-tests, we have found that the distribution of self-tests does not tend to be a public activity. We do not anticipate, based on other studies that it will be common for men to approach with numerous requests for self-tests, but will have contingencies and messaging in place to handle these situations should they occur.

Incentives. A risk stems from the use of incentives to promote confirmatory testing and linkage to care. However, the value of the incentives will be relatively low – on par with certain costs of confirmatory testing such as transportation and opportunity costs. This means that most participants are unlikely to experience a significant economic gain because of coming for confirmatory testing, thereby minimizing the risk of coercion. A recent publication by the Ethics Working Group of HPTN has also made the case that the use of incentives for health promotion does not necessarily undermine individual autonomy. Instead, the incentives can help overcome economic obstacles or motivational deficiencies; they can promote engagement in health-related behaviors that participants regard as beneficial or worthwhile, but do not undertake due to behavioral biases such as present-biased preferences. Our experience implementing small economic incentive interventions in Kenya and Uganda has also demonstrated that such interventions are acceptable to both communities and ethical review boards.

In addition, we will ensure that our training session for network-central promoters, including messaging to participants promoting confirmatory testing or linkage to care or to prevention, includes a component on the importance of maintaining privacy and confidentiality and the rights of all individuals to choose whether, when, how, and to whom to disclose their HIV status. Our prior experience in Kenya implementing interventions among HIV-infected adults who are receiving ART, and on the nature and pathways of stigma and stigma reduction, shows that the risk of stigma and inadvertent disclosure can be minimized. As a result, we expect the risk of inadvertent disclosure of HIV status because of study participant to be very rare.

Behavioral and social network research. In this study, we will be conducting survey questionnaires and indepth semi-structured interviews among adult men only (ages 18 and older) working in fishing or fishing-related occupations. Aim 1 begins with a BMU census/registry verification and updating at participating beach landing sites to identify and enumerate the population of men registered as working in the fishing industry currently registered as working at the beach-landing site. This will involve collection of non-sensitive data including residency, confirmed occupation in fishing, and age. The baseline survey for Aim 1 will include questions about participants' perceived personal risk and perceived severity of HIV infection; self-reported sexual behavior, as well as marital and partnership status, sero-concordant or discordant couple status; prior HIV testing history; knowledge, attitudes, beliefs, and self-efficacy related to HIV care and prevention behaviors (specifically, usage of PrEP or ART); socio-demographic characteristics; and members of close social networks.

Under Aim 1, the 3-month follow up surveys will be used to assess HIVST experiences and to verify selftest usage, and to measure the sexual and health behaviors of men who do and do not accept self-tests or vouchers. Qualitative key informant interviews with a small sample of network promoters will include questions about men's experiences offering self-tests to the men in their close social networks (intervention group) or offering vouchers to exchange for self-tests at local clinics (comparison group). Under Aim 2, A small sample of respondents will be selected for recruitment for in depth interviews that explore in greater depth, the dimensions of ART and PrEP decision-making including perceptions of risk and severity of HIV disease, beliefs about efficacy of ART and PrEP, and other factors in the individuals' lives (occupational mobility, relationship context and dynamics, community norms and dynamics, and perceptions of local health care services) that influence the decision whether or not to self-refer for confirmatory testing and enrollment in ART, or PrEP eligibility screening and uptake.

Under Aim 3, qualitative in-depth interviews will explore factors that affect participants' motivations and ability to stay engaged in HIV care and prevention programs.

As with all collection of data on sensitive topics, there is a risk of emotional discomfort that may accompany disclosure of potentially stigmatized behaviors. To minimize this risk, we will use the procedures we have previously used in several studies in the setting that we have conducted that involved collection of sensitive information; these are described in the sections that follow.

